15.1.2 Blood and Lymphatic System Disorders

Reporting will be done for SAF.

Any adverse event preferred term belonging to the MedDRA SOC="Blood and Lymphatic System Disorders" will be selected.

Statistics as presented for section 15.1.1, Serious Adverse Events Related to Cladribine, will be repeated.

15.1.3 Neoplasms Benign, Malignant, and Unspecified

Reporting will be done for SAF.

Any adverse event preferred term belonging to the MedDRA SOC="Neoplasms Benign, Malignant, and Unspecified" will be selected.

Analyses as presented for SOC="Blood and Lymphatic System Disorders" will be repeated.

15.1.4 Lymphopenia

Unless specified, reporting will be done for the Lymphocyte Analysis Population.

Evolution of absolute lymphocyte count (ALC) and specifically lymphopenia is of primary interest for treatment with cladribine.

ALC will be tabulated by grade using the NCI-CTCAE version v3.0, and lymphopenia grades are defined as follows:

Table 6 NCI-CTCAE Lymphopenia Grade

Laboratory Toxicity	Grade 1	Grade 2	Grade 3	Grade 4
ALC Decreased	<LLN – 800/mm ³ <LLN – 0.8 x 10 ⁹ /L	<800 – 500/mm ³ <0.8 – 0.5 x 10 ⁹ /L	<500 - 200/mm ³ <0.5 – 0.2 x 10 ⁹ /L	<200/mm ³ < 0.2 x 10 ⁹ /L

Change from first cladribine/placebo dose

Data collected from first cladribine/placebo dose [Study Day 1] to the last ALC value in PREMIERE will be presented and summarized on a continuous manner (change from Study Day 1 and absolute value) and by grade, over time.

ALC Study Baseline is defined by the latest ALC value prior or equal to first cladribine/placebo dose [Study Day 1].

Over-time target point will be presented using visit window computed relative to Study Day 1, as presented below.

In case multiple samples are collected in the same window, the value closest to the target day will be used for analysis, where the target day is the middle of the time window. If there are two values with the same time before and after the target day, the earlier (first) value will be used for analysis.

Table 7 Time window for lymphocyte from first cladribine/placebo dose

Evaluation	Target point (day)	Interval for analysis (Day)
ALC Study Baseline	Study Day 1	Last value prior to or equal to Study Day 1
Week 2	14	[2 ; 23]
Week 5	35	[24 ; 47]
Week 9	63	[48 ; 77]
Week 13	91	[78 ; 103]
Week 16	112	[104 ; 130]
Week 24	168	[131 ; 203]
Week 36	252	[204 ; 287]
Week 44	308	[288 ; 329]
Week 48	336	[330 ; 350]
Week 52	364	[351 ; 376]
Week 55	385	[377 ; 399]
Week 60	420	[400 ; 461]
Week 72	504	[462 ; 546]
Week 84	588	[547 ; 630]
Week 96	672	[631 ; 686]
Week 101	707	[687 ; 721]
Week 105	735	[722 ; 784]
Week 120	840	[785 ; 924]
Week 144	1008	[925 ; 1092]
Week 168	1176	[1093 ; 1260]
Week 192	1344	[1261 ; 1428]
Week 216	1512	[1429 ; 1596]
And every 24 weeks.... If needed		

Change from the end of clinical trial

A summary table of ALC similar to change from first cladribine/placebo dose will be presented.

Data collected from last value from the end of clinical trial to the last ALC value in PREMIERE will be presented and summarized on a continuous manner (absolute value only) and by grade, over time.

ALC Registry Baseline is defined as the first ALC date with a value on or after the end of clinical trial +1 day [Registry Day 1].

Programming rule to cover possible unclean data:

If first ALC date in PREMIERE is before the end of clinical trial, ALC Registry Baseline is defined as the first ALC value in PREMIERE on or after the end of clinical trial + 1 day.

A new set of time window are presented below using visit window computed relative to ALC Registry Baseline.

If more than 1 value is available for a particular time window for the same subject, the first value in the time window will be considered.

Table 8 Time window for lymphocyte from the end of clinical trial

Evaluation	Interval for analysis (day)
Last value from last clinical trial	
ALC Registry Baseline	First ALC date with value in PREMIERE registry
Week 12	[2 - 98]
Week 24	[99 - 182]
Week 36	[183 - 266]
Week 48, 1y	[267 - 350]
Week 60	[351 - 434]
Week 72	[435 - 518]
Week 84	[519 - 602]
Week 96, y2	[603 - 700]
Week 144, y3	[701 - 1036]
Etc.	[1037 - weekN*7+4*7]

Lymphopenia grade and MS-DMD

Best and Worst ALC grades will be presented in relation to use of MS-DMD medication. For subjects with MS-DMD medications reported at least once after end of clinical trial, the best and worst ALC grade will be selected on or after (\geq) the first MS-DMD.

The Worst and the Best grade will be summarized overall and by treatment group. Subjects who are not taking MS-DMD from the end of clinical trial +1 day to the end of PREMIERE will be excluded from the analysis.

Resolution of lymphopenia computed with observed ALC value

Subjects who complete or drop out at the end of the clinical trial with an unresolved lymphopenia will be presented, together with their outcome in PREMIERE registry. The outcome can be resolved or unresolved.

An unresolved lymphopenia is defined for a subject who left the end of a clinical trial without returning to normal or grade 1 ALC value after an episode of grade 3 or 4 lymphopenia. A grade 3 or 4 lymphopenia episode is defined by a start/end date. Start= ALC \geq grade 3, post baseline, End = following normal (grade 0) or grade 1.

The duration (in months) of the resolved episodes (out of the unresolved at end of clinical trial period) will be summarized. In addition, use of MS-DMDs prior to resolution will be presented.

Resolution of lymphopenia computed using CRF tick box

Reporting will be done for SAF. This is an exception, to include the largest possible information available.

The number of subjects with declared Grade 3 or 4 lymphopenia at end of clinical trial [CRF Tick box], will be summarized together with their outcome in PREMIERE. The outcome in PREMIERE will be computed from those with at least one grade 0/1 in PREMIERE or with a CRF "resolution date".

Presentation per treatment group and total will be done.

Resolution of lymphopenia based on observed ALC value versus CRF tick box

A 2-by-2 table of number of subjects with and without resolution of lymphopenia at the end of clinical trial based on ALC value versus CRF Tick box will be presented.

In addition, a listing will be generated for subjects with unresolved lymphopenia at the end of clinical trial according to ALC grade, but with the CRF Tick box = "Resolved". The following variables will be displayed: Subject ID, cumulative dose of cladribine, previous clinical trial, treatment group (see section 9.1), all ALC values in PREMIERE with grade and date and tick box for resolved with date of resolved if available.

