## 8.4 Follow-Up Interviews

For MS subjects, the information to be ascertained in the follow-up interviews fall into five main categories:

- Updates in contact information
- Occurrence of SAEs (including time of event and outcome)
- Occurrence of AEs in the ‘Blood and Lymphatic System Disorders’ and ‘Neoplasms Benign, Malignant, and Unspecified’ SOCs (including time of event and outcome)
- Capture of any lymphocyte count assessments performed since last visit
- Prescription of immunosuppressant medications including type and start date

It is expected that subjects in PREMIERE will attend their routine MS care visits. The PRP is expected to request blood count and differential if lymphopenia has not resolved (i.e., lymphocyte count is equal or greater than  $0.8 \times 10^9/L$ ). All lymphocyte count results will be captured by the PRP regardless of monitoring frequency. Participating PRP will be instructed to have blood count and differential performed at least yearly until resolution of lymphopenia (i.e., a Grade 1 or Grade 0 lymphopenia), or end of the study period.

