9.1 Treatment groups

Analyses will be performed on the "as treated principle", where patients are allocated to the treatment group that they actually received in the clinical trial studies (which may be different from the study treatment to which they were randomized to).

Patients are assigned to the following treatment groups according to their actual treatment in one of the studies CLARITY alone, ONWARD, CLARITY/CLARITY EXTENSION, ORACLE MS, Pantoprazole DDI.

- **Never exposed to cladribine:** if a subject has taken only placebo (or placebo +IFN-β) in studies, then her/his data becomes part of the "Never exposed to cladribine" treatment group. A subject who switches treatment from placebo to cladribine in subsequent studies/periods **will not** be considered in this group.
- **Exposed to cladribine:** patients with at least one dose of cladribine. Subjects who were on placebo during the clinical trial and switched to cladribine in the extension study will contribute to the treatment group "Exposed to cladribine" from the moment they initiate cladribine.

An example of the header for table outputs is presented below.

Table 2 Table header example

	Never exposed to Cladribine (N=XXXX)	Exposed to Cladribine (N=XXXX)	Total (N=XXXX)
Safety Analysis Population	xxx (100.0)	xxx (100.0)	xxx (100.0)

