12.2 Medications in PREMIERE

Reporting will be done for SAF.

Medications in PREMIERE are medications (other than cladribine or placebo medications) which are taken by subjects at any time after (>) the end of clinical trial.

Data collection will be derived from PREMIERE dataset Concomitant Medication panel (SDTM.CM). Specifically, medications used during pregnancy collected for female partner of male patients will not be included (SDTM.CM CMCAT = “over the counter medications”, “prescription medications”).

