12.4 Handling of Partial dates for Medications

Missing and partial dates will be imputed considering the fact that medication may be considered as medication taken concomitantly to PREMIERE registry.

- Start missing day will be imputed to be 1 and start missing month will be imputed to be January.
- End missing day will be imputed to be the last day of the month. End missing month will be imputed to the last month of the year. In case of death, imputation rules will assure that no end dates are imputed after death.
- No imputation for complete start date and end date missing (day, month and year), and therefore medication will be ignored.

- If start date is completely missing (i.e. day, month, year missing) and end date is known or partially known then the start date will be imputed to be the Registry Day 1 minus one day if prior to end date, otherwise equal to end date.
- Complete end date missing (day, month and year) and partial or complete start date then will be imputed to be the last study assessment date.

13 Study intervention Compliance and Exposure

Not Applicable (please see section 7).

14 Efficacy Analyses

Not Applicable.

15 Safety Analyses

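### SAP 15.1.4 orders MS-DMD start against lymphocyte counts and resolution using earliest-possible imputed dates and no floor at Registry Day 1, so counts taken before the drug can be tabulated as after it

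*SAP*

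**What the plan says.** Five rules combine here.

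- **Entry and window (SAP 15.1.4, Lymphopenia grade and MS-DMD).** The rule reads: "For subjects with MS-DMD medications reported at least once after end of clinical trial, the best and worst ALC grade will be selected". The window opens at the first MS-DMD, that date included. No end of window and no lower bound are written.
- **What counts as a registry medication (SAP 12.2).** These are drugs "which are taken by subjects at any time after" the end of the clinical trial. The test is on taking, not on starting, so a drug begun earlier and continued qualifies.
- **Partial start dates (SAP 12.4).** "Start missing day will be imputed to be 1 and start missing month will be imputed to be January". If the start date is wholly missing but the end date is at least partly known, the start becomes the day before Registry Day 1, or the end date if that is not later. Under SAP 9.6 the day before Registry Day 1 is the last trial day.
- **ALC periods (SAP 9.2).** Period 1 runs from the first trial dose and so contains trial counts. Period 2 starts at the first registry count. The DMD paragraph names neither.
- **Resolution (SAP 15.1.4, observed ALC value).** After the duration summary the plan adds: "In addition, use of MS-DMDs prior to resolution will be presented".

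SAP 15.1.4 gives no separate date rule for DMDs, so I take the SAP 12.4 dates to apply.

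**The concern.** SAP 12.4 says that its imputation is made with a view to whether a drug may have been taken concomitantly with the registry. For that purpose the earliest possible start is a cautious choice. In SAP 15.1.4 the same date does another job: it decides whether a lymphocyte count, or a resolution, came before or after the drug. There the earliest possible start is not neutral, because every error runs the same way and places the drug too early.

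Best and worst grades are extremes, so one wrongly admitted count can set them. Widening the window backwards can only leave the worst grade unchanged or worsen it, and can only leave the best grade unchanged or improve it. For resolution, the same shift can only add to the number shown as using an MS-DMD beforehand.

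The absence of a floor stands out because the preceding paragraphs of SAP 15.1.4 do set one at Registry Day 1 for the ALC Registry Baseline, with a programming rule for unclean dates. These DMD displays are where a reader will look to see whether later treatment accompanies low counts or recovery.

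**Working it through.** The plan states no figure for this analysis, so there is nothing to reproduce. I traced the date rules and then sized the shift under stated assumptions.

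**1. Size of the shift.** With the month missing and the true start spread evenly over a 365-day year, the offset from 1 January runs from 0 to 364 days, with mean 364/2 = 182 (maximum 365 in a leap year). With only the day missing, in a 31-day month, it runs from 0 to 30 days, with mean 15.

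**2. Trace with an assumed trial end of 15 October 2008** (Registry Day 1 = 16 October 2008). Trial days admitted are counted from the window start to trial end inclusive. They matter only if trial ALC values are in the pool; case (a) also needs first to mean first ever.

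| Case | Window start as written | Trial days admitted | Start with floor |
|---|---|---|---|
| (a) Started 1 Mar 2008, continued | 1 Mar 2008 | 229 | 16 Oct 2008 |
| (b) True start 20 Nov 2008, year only | 1 Jan 2008 | 289 | 16 Oct 2008 |
| (c) True start 20 Oct 2008, day missing | 1 Oct 2008 | 15 | 16 Oct 2008 |
| (d) Start wholly missing, later end date known | 15 Oct 2008 | 1 | 16 Oct 2008 |
| (e) True start 20 Nov 2009, year only | 1 Jan 2009 | 0 | 1 Jan 2009 |

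Case (e) admits no trial count, but it still admits counts from 1 January to 19 November 2009 that precede the drug. The floor does not cure that.

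**3. How often a year-only date reaches into the trial.** For a DMD truly started after the trial, 1 January falls in the trial only if the start year equals the trial-end year. Take trial end uniform over the year and the start uniform over the next L years. The probability is 1 − L/2 for L ≤ 1 and 1/(2L) for L ≥ 1:

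- L = 0.5: 1 − 0.25 = 75%
- L = 1: 50%
- L = 2: 25%
- L = 4: 12.5%
- L = 8: 6.25%

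A simulation of 200,000 draws per case gave 0.750, 0.498, 0.251, 0.124 and 0.062. When the date does reach in, about 120 to 140 trial days are admitted on average.

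**4. Reaching the nadir.** Protocol section 3 reports a nadir at Week 55 in CLARITY. SAP Table 7 puts Week 55 at day 385 and Week 96 at day 672, which is 672 − 385 = 287 days apart. If the trial ended at Week 96 (an assumption), imputation reaches back that far in 0.3% (L = 8) to 5% (L = 0.5) of year-only records.

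**5. Order against resolution.** This step does not depend on trial counts. If the DMD start and the resolution are independent and uniform within one year, the chance that the DMD came after resolution is 0.5. With the start set to 1 January, essentially all are classed as before. About half of such year-only records are then wrong.

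**The case against.** The case on the other side is substantial.

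- **The text can be read benignly.** Entry is defined by DMD use after trial end, so the first MS-DMD may mean the first of those. The paragraph follows the registry-based table, and Period 2 may be intended, in which case no trial count enters. This stands: a reader might infer that cladribine-period counts *are* reported as post-DMD, but the documents support only that they *can* be.
- **The interferon example is thin.** Interferon beta is in SAP Table 5, but the documents show it given in a trial only in the never-exposed definition of SAP 9.1: "if a subject has taken only placebo (or placebo", where the bracket goes on to name it. Its use alongside cladribine is not documented. Where a DMD truly began in the trial, later counts really do follow it; the difficulty is overlap with the trial treatment, not false order.
- **The primary result is untouched.** Resolution status and episode duration use ALC grades, ALC dates and CRF entries, never a DMD date. No inference is planned (SAP 9.14).
- **Start dates are collected.** Protocol 8.4 lists "Prescription of immunosuppressant medications including type and start date", and queries are to be resolved as far as possible before lock (SAP 6.2). Partial dates may be few. Against that, lag-interval data are gathered retrospectively, some directly from subjects (Protocol 8.1 and 8.3.1).
- **Stop dates are not the issue.** The grade window is open-ended whatever the end date.

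None of this answers the ordering problem. Followed as written, SAP 12.4 places a year-only start before virtually any count or resolution of that year. Case (e) shows this with no trial data involved.

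**Conclusion.** The point holds as a defect in how two descriptive MS-DMD displays are specified. Counts taken before the true DMD start, mostly post-trial counts and trial counts only if Period 1 supplies the values, can be shown as post-DMD. A year-only DMD start in the resolution year is called use before resolution regardless of the true order.

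The size per affected record is about 182 days on average for a year-only date and about 15 days for a missing day, assuming evenly spread starts. About half of same-year orderings would be wrong if the order is random. The documents give neither the number of partial dates nor the spread of DMD starts, so the total effect is unknown, and the shares in the working are illustrative.

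A reader might go further and infer that the tables transfer the cladribine nadir to the DMD and so favour cladribine. The documents do not support that. Reaching the nadir by imputation is uncommon under the assumptions tried, results are also shown for the never-exposed group, and no direction of bias is established. The display supports the second primary endpoint (time to resolution of lymphopenia) but does not alter it. The change is nevertheless worth making, because the rule is wrong for this purpose and cheap to correct.

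**What to change.** In SAP 15.1.4:

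1. Define first MS-DMD (first ever, or first after trial end).
2. Start the window at the later of the DMD start and Registry Day 1, and use only ALC values on or after that date. This also settles the choice of ALC period, since trial counts then drop out.
3. Show subjects whose DMD was already ongoing at trial end separately from those who newly started one.
4. For ordering DMD start against an ALC or resolution date, do not use the SAP 12.4 imputation. Classify as before, after, or order not determinable from the known date parts.
5. Add a sensitivity run with each partial start set to its latest possible date.

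SAP 12.4 can stay as it is for deciding whether a drug counts as a registry medication. Steps 2 and 4 are both needed: the floor keeps trial counts out, and the classification deals with post-trial counts and resolutions.

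The cost is a few sentences of SAP text and minor programming. The downside is that some subjects, probably few but not countable from the documents, move to an order-not-determinable row.

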8.2 Definition of Analysis Populations and Subgroups

The registry target population includes all subjects who participated in Sponsor oral cladribine Phase I to III clinical trials in MS associated with a protocol approved prior to the time of submission of the marketing application and completed (last patient, last visit) after November 2008. This corresponds to five clinical trials (protocol number/study name):

- 25643/CLARITY
- 26593/ONWARD
- 27820/CLARITY EXTENSION
- 27967/Pantoprazole DDI
- 28821/ORACLE MS

Subjects will be analyzed according to their actual exposure to oral cladribine. There will be no per-protocol analysis population excluding patients with protocol deviations.

Safety Analysis Population (SAF)

The Safety Analysis Population will consist of all subjects from studies CLARITY, CLARITY EXT, ORACLE MS and ONWARD who are enrolled in the PREMIERE registry as full participants.

Lymphocyte Analysis Population

The lymphocyte analysis population consists of all subjects from SAF with at least one absolute lymphocyte count (ALC) value in PREMIERE, with an associated ALC date after the end of clinical trial.

DDI Safety Set

The **DDI** Safety Set will include all subjects from the Pantoprazole DDI study who are enrolled in the PREMIERE registry as full participants. In this study, subjects received two single doses of 10 mg cladribine separated by a wash-out of at least 10 days and two 40 mg doses of pantoprazole on two consecutive days. Data from the DDI Safety Set will be presented in listings only.

9 General Specifications for Data Analyses

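### The observed-count lymphopenia resolution table omits subjects never re-tested after the trial, and the tick-box table does not say how it classes them

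*SAP*

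**What the plan says.** SAP section 5 assigns the primary endpoint on resolution of lymphopenia to section 15.1.4. That section opens with a default: "Unless specified, reporting will be done for the Lymphocyte Analysis Population". Section 8.2 limits this population to SAF subjects with "at least one absolute lymphocyte count (ALC) value in PREMIERE, with an associated ALC date after the end of clinical trial".

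Two resolution tables follow.

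- **Observed ALC.** A subject enters if he or she "left the end of a clinical trial without returning to normal or grade 1 ALC value after an episode of grade 3 or 4 lymphopenia". No other population is named, so the default applies. The outcome has two levels: "The outcome can be resolved or unresolved". The accompanying time measure covers resolved episodes only: "The duration (in months) of the resolved episodes (out of the unresolved at end of clinical trial period) will be summarized".
- **CRF tick box.** Subjects enter if grade 3 or 4 lymphopenia was declared at trial end. Here the population is changed: "Reporting will be done for SAF. This is an exception, to include the largest possible information available". The outcome rule is "The outcome in PREMIERE will be computed from those with at least one grade 0/1 in PREMIERE or with a CRF" resolution date. What happens to everyone else is not stated.

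A 2-by-2 table then compares the two sources at trial end, and a listing covers subjects unresolved by ALC but ticked as resolved.

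Three general rules bear on this. SAP 9.12 rules out imputation. SAP 9.13 keeps missing observations in the denominator as their own category, but that denominator is the analysis set in use. SAP 10.1 reports the size of the Lymphocyte Analysis Population against the SAF.

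**The concern.** Whether a subject left the trial with unresolved lymphopenia is settled by trial data. No registry count is needed. The observed-ALC table nevertheless admits only subjects who were tested later, so its denominator depends on something that happens after the starting point. If re-testing is related to recovery, in either direction, the resolved percentage does not describe the group that left the trial unresolved.

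Subjects without a later count are foreseeable. Protocol 8.4 obtains counts through routine care, with physicians instructed to test at least yearly. Protocol 8.1 expects some subjects to have no accessible record for the period between trial and registry. For those subjects, the lag questionnaire in protocol 8.3.1.1 records lymphocyte status only as normal, abnormal or unknown, which may leave no value that satisfies section 8.2.

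A reader who sees two different resolution percentages will probably put the gap down to laboratory value versus CRF entry. Part of it may come from missing tests, and neither the 2-by-2 table nor the one-directional listing separates that part out.

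**Working it through.** The plan states no resolution percentage, number unresolved at trial end or number untested, so there is no figure to reproduce. The check has two parts.

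**1. Following a subject through the rules.** Take a subject who qualifies for both tables.

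| After the trial the subject has | Observed-ALC table | Tick-box table |
|---|---|---|
| A grade 0/1 count | Resolved | Resolved |
| Counts, none grade 0/1, with a CRF resolution date | Unresolved | Resolved |
| Counts, none grade 0/1, no CRF date | Unresolved | Not stated |
| No count, with a CRF resolution date | Absent | Resolved |
| No count, no CRF date | Absent | Not stated |

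The second row is a true difference of source. The last two rows are missing tests. SAP 9.13 cannot bring those subjects back into the observed-ALC table, because a subject outside the analysis set cannot be counted as missing within it. In the tick-box table 9.13 can operate, and it would point to a separate missing category.

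The tables also differ in who enters. A subject at grade 2 on leaving the trial, after a grade 3 or 4 episode, qualifies for the observed-ALC table. The tick-box table needs grade 3 or 4 declared at trial end.

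**2. Illustrative size.** All inputs are assumptions, and both tables are given the same entrants for simplicity.

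- p = resolved share among tested subjects, set at 0.80
- m = share with no post-trial count, set at 0.10, 0.20 and 0.30
- r = share of untested subjects with a CRF resolution date, from 0 to 1

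The observed-ALC share is p, whatever m is. Over all entrants, the lower bound (untested all unresolved) is p(1 − m) and the upper bound (untested all resolved) is p(1 − m) + m.

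| m | Observed-ALC table | Lower bound | Upper bound |
|---|---|---|---|
| 0.10 | 80% | 0.80 × 0.90 = 72% | 72 + 10 = 82% |
| 0.20 | 80% | 0.80 × 0.80 = 64% | 64 + 20 = 84% |
| 0.30 | 80% | 0.80 × 0.70 = 56% | 56 + 30 = 86% |

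The width of the bounds equals m and does not depend on p. With m = 0.20, p = 0.70 gives 56–76% and p = 0.90 gives 72–92%.

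If the tick-box table did class the remainder as unresolved, its share would be p(1 − m) + mr, and the gap between the tables would be p − [p(1 − m) + mr] = m(p − r). At m = 0.20 and p = 0.80:

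- r = 0: 0.20 × 0.80 = 16 points
- r = 0.5: 0.20 × 0.30 = 6 points
- r = 0.8: zero
- r = 1: 0.20 × (−0.20) = −4 points, so the order reverses

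**The case against.** The best defence is that a table of outcomes computed from observed counts needs a count. The SAP bars imputation, discloses the change of population in the second table and explains it. Section 10.1 will show how many SAF subjects lack a post-trial count. No inference is planned, and best- and worst-case bounds are a matter of preference in a descriptive registry.

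Much of this is fair. The restriction has a rationale, and bounds are optional. But a subject without a count can be shown as such without imputing anything, and section 10.1 does not break the number down for subjects unresolved at trial end. The wider population in the second table suggests that the SAP recognised the loss, yet the observed-ALC table was left as it was.

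A reader might also infer that untested subjects are counted as unresolved in the tick-box table, so that one table is optimistic and the other pessimistic. The SAP does not say so. The two-level sentence belongs to the observed-ALC part only, a CRF resolution date makes an untested subject resolved, and 9.13 points to a separate category for the others. As the working shows, the gap can vanish or reverse.

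**Conclusion.** The point holds for the observed-ALC table: the rules in 8.2 and 15.1.4 together make its resolved share conditional on later testing. For the tick-box table the defect is narrower: the class of subjects with neither a grade 0/1 value nor a CRF date is not specified. Differences between the tables may therefore mix data source, entry criteria and missing tests.

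The size and direction are unknown because the documents do not report how many subjects were untested. The 72–82% to 56–86% range only shows what 10–30% untested would do at 80% resolution among those tested.

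A reader might go further and conclude that this is why the tables fail to describe the primary endpoint. That is not supported. The endpoint is a time to resolution (protocol 6.1), which no percentage can describe, however untested subjects are classed. That loss comes from the change declared in SAP section 7, Table 1, from life-table methods to descriptive statistics. In a time-to-event analysis starting at trial end, subjects with no later count would be censored at time zero and would add nothing. Omitting them matters because the summary is now a percentage. This is a cheap improvement to the table, not a repair of the endpoint.

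**What to change.** Run the observed-ALC resolution table on all SAF subjects with unresolved lymphopenia at the end of the trial, as a second stated exception to the default population. In both tables show three outcomes:

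1. resolved;
2. tested and not resolved, with last grade and date;
3. no post-trial result.

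Show a CRF resolution date without a count separately, as resolved by CRF only. Give the resolved share over all entrants. Bounds that treat the untested as all unresolved or all resolved can be added.

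The cost is a short change of SAP wording and one more table row. The reported resolved percentage may be lower or less precise. The change uses data already collected and does not reinstate time to resolution.
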